### **Statistical analysis**

Categorical variables will be presented as numbers (percentages), whereas continuous variables will be expressed as the means  $\pm$  standard deviations. Overall *P* values for categorical and continuous parameters will be obtained by Fisher's exact test and Kruskal-Wallis test, respectively. Pairwise comparisons among all groups were performed when the overall group effect was significant. Agreement between the blinded raters will be tested with Fleiss kappa. For mucus production quantity, the 2-category scale (minimal [score 0-1] vs. moderate [score 2-4]) will be examined. Potential risk factors for mucus production include female sex, lower body mass index, prior abdominal or pelvic surgery, poor bowel preparation, water as the infused solution, larger volume of infusion, and longer insertion time. Univariate and multivariate logistic regression analyses will be used to assess which of the demographic and procedural data are independent predictors of moderate mucus production. Factors with a *P* value  $< 0.1$  on univariate analysis will be further entered in the multivariate logistic regression analysis. The odds ratio with 95% confidence

interval will be used to describe the influence of various factors on mucus production. All statistical analyses will be performed by using SAS version 9.3 or later (SAS Institute Inc., Cary, NC, USA). The criterion for statistical significance will be a *P* value <0.05.

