### **Outcomes**

The primary outcomes are the left colon mucus scores using CMS between colonoscopy using CO2 insufflation and WE, and, in those patients undergoing WE, the scores between groups using water versus 50% saline versus 25% saline. Secondary outcomes include procedure times (insertion and withdrawal times) and acute serum electrolyte abnormality in the WE saline groups. Patients assigned to the WE saline groups will receive measurements of the serum sodium, potassium, and chloride, which will be performed 20 minutes before and 60 minutes after the colonoscopy.

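### The arm comparisons are valid but unadjusted; a pre-specified model with sex, BMI and prior surgery would recover a modest amount of precision at little cost

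*Combined protocol and SAP*

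**What the plan says.** In the combined protocol and SAP, Statistical analysis, overall P values for "categorical and continuous parameters will be obtained by Fisher's exact test and Kruskal-Wallis test, respectively". The follow-up step reads "Pairwise comparisons among all groups were performed when the overall group effect was significant"; no test, covariates or effect estimate is given for it. The Randomization section states a 1:1:1:1 allocation and no stratification factors.

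The Statistical analysis section also lists seven candidate drivers of mucus. Three are patient characteristics: "Potential risk factors for mucus production include female sex, lower body mass index, prior abdominal or pelvic surgery". The other four are the quality of preparation, the use of water as the fluid, the volume infused and the time taken to insert. The regression is described thus: "Univariate and multivariate logistic regression analyses will be used to assess which of the demographic and procedural data are independent predictors of moderate mucus production". Under its entry rule, anything reaching P < 0.1 "on univariate analysis will be further entered in the multivariate logistic regression analysis", and odds ratios with 95% CIs are reported.

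The Outcomes section makes two sets of contrasts primary: CO2 insufflation against water exchange (WE), and water against 50% and 25% saline within WE.

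**The concern.** The plan expects certain patient characteristics to predict the primary outcome, but neither the allocation nor the arm comparison uses them. If they matter, a comparison that adjusts for them has more power and gives a tighter estimate.

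The regression looks as if it might supply the adjusted estimate, but it answers another question. No planned analysis therefore estimates the primary arm contrasts adjusted for baseline factors alone. What is at stake is some power, mainly for contrasts smaller than the design effect, and an adjusted effect size with a confidence interval for each contrast.

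**Working it through.** **1. Sorting the seven listed factors**

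| Factor | When determined | Suitable for adjusting the arm effect? |
|---|---|---|
| Sex, BMI, prior abdominal or pelvic surgery | Before allocation | Yes |
| Bowel preparation quality | Scored at the procedure | Not safely |
| Water as the infused solution | The treatment itself | It is the exposure |
| Infused volume | During the procedure, after allocation | No |
| Insertion time | After allocation; also a secondary outcome | No |

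The single water term, as worded, separates water from everything else. It gives no estimate of 50% versus 25% saline or of CO2 versus WE. Under the P < 0.1 rule the baseline factors, or the water term itself, may drop out.

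**2. The plan's own sample size**

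Inputs from Sample size estimation: 50% vs 80% with CMS score 1 or below, alpha 5% (taken as two-sided), power 90%.

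n = [1.960 × √(2 × 0.65 × 0.35) + 1.282 × √(0.5 × 0.5 + 0.8 × 0.2)]² / 0.30² = (1.322 + 0.821)² / 0.09 ≈ 51, or 52 per group with the usual rounding. With a continuity correction the result is 58, and Fisher's exact test also needs about 58. The stated 68 is therefore not reproduced. That is a separate matter and errs towards a larger trial. The inflation does reproduce: 68 × 1.10 = 74.8, or 75. I use 68 evaluable patients per arm below.

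**3. The planned test, by exact enumeration at 68 per arm, two-sided 5%**

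- 50% vs 80%: Fisher power 95.0%.
- 50% vs 70% (assumed; not in the plan): Fisher power 60.0%.
- 50% vs 50%: Fisher's actual type I error is about 3.2%, so the test is conservative.

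**4. Adding the baseline covariates**

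The documents give no covariate strengths, so these are assumptions: 50% women, standardised BMI, 25% with prior surgery, and a range of odds ratios (ORs). Marginal rates were held at target. The simulation used 2,000 trials per row, giving a Monte Carlo standard error of about √(0.6 × 0.4 / 2,000) = 1.1 points near 60%. The adjusted test is a logistic likelihood-ratio test.

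| Rates | Assumed OR | Fisher | Chi-square | Adjusted | Adjusted − Fisher | Adjusted − chi-square |
|---|---|---|---|---|---|---|
| 50/80 | 1.0 | 95.2 | 97.2 | 96.8 | 1.7 | −0.4 |
| 50/80 | 1.5 | 95.0 | 96.8 | 96.9 | 1.9 | 0.2 |
| 50/80 | 2.0 | 95.9 | 97.0 | 97.7 | 1.8 | 0.7 |
| 50/80 | 3.0 | 94.7 | 96.5 | 97.9 | 3.2 | 1.4 |
| 50/70 | 1.0 | 59.1 | 65.1 | 66.2 | 7.1 | 1.1 |
| 50/70 | 1.5 | 60.3 | 67.1 | 68.3 | 8.1 | 1.2 |
| 50/70 | 2.0 | 58.4 | 65.2 | 68.5 | 10.1 | 3.3 |
| 50/70 | 3.0 | 58.4 | 65.5 | 73.0 | 14.7 | 7.5 |

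(Differences are taken before rounding.) A second simulation of 3,000 trials used ORs from 1.5/1.25/1.5 to 2.5/1.8/2.5 for sex, BMI per SD and surgery. At 50% vs 70% it gave 59–61% for Fisher and 68–72% adjusted, with adjusted type I error of 5.0%. Over that span the gain over Fisher is about 9 to 13 points; the most extreme OR in the table takes it to nearly 15. The column that isolates the covariates shows about 1 to 7 points.

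**5. Chance imbalance**

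With 75 per arm and 50% women, the probability that a given pair of arms differs by 10 points or more in share of women is 2 × [1 − Φ(0.10 / √(2 × 0.25 / 75))] = 2 × [1 − Φ(1.22)] ≈ 22%. At a risk near 50%, such an imbalance would shift the CMS outcome by about 1.0 point (sex OR 1.5) to 2.3 points (OR 2.5), against a design difference of 30 points.

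**6. Does an ordinary logistic model break in an extreme arm?**

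The documents give no CO2 rate; suppose it is 98–99%. The chance that all 68 patients in the arm score 1 or below is 0.98^68 = 25% or 0.99^68 = 50%. By enumeration, counting empty cells as non-significant for the unadjusted logistic Wald test:

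- 80% vs 98%: Fisher 93%, Wald 69%.
- 85% vs 99%: Fisher 85%, Wald 38%.
- 50% vs 98%: Fisher about 100%, Wald 75%.

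An adjusted model tested by Wald could therefore lose far more than adjustment gains.

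**The case against.** The best defence is that nothing here is an error. Under randomisation the unadjusted tests are valid, and their type I error already allows for chance imbalance. That stands. A reader might infer that imbalance biases the primary comparison; the documents do not support it, and step 5 shows the likely shift is small.

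The defence also notes that power at the design effect is already 95% with Fisher, and exceeds 99.9% at the pilot rates of 24% vs 82% in Table 1. That stands too: the water versus 50% saline conclusion is not at risk on the plan's own figures. The larger gain needs a 50% vs 70% contrast that the plan does not state, and most of it comes from replacing Fisher's test. Nor would adjustment rescue the 50% versus 25% saline comparison. At the pilot rates of 82% vs 77%, approximate power at 68 per arm is 10.8%, rising only to 13.6% if covariates explained 30% of the variance (68 / 0.70 = 97.1 effective patients per arm).

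A reader might also infer that no adjusted analysis is planned. That is too strong: the regression is planned, infused solution is a candidate, and ORs with CIs will be reported. Nor does the plan say that this model will condition on volume and insertion time; they enter only if they pass P < 0.1.

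Finally, the listing of recorded information under Colonoscopy Procedures does not name sex, BMI or prior surgery. Their collection is inferred from the regression that needs them. None of this removes the gap, but it makes the gap minor.

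**Conclusion.** The point holds as a minor matter of efficiency. The arm comparisons forgo some precision although the plan names three usable baseline factors, and the risk-factor regression does not estimate the randomised contrasts.

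The size is about 1 to 3 power points over Fisher at 50% vs 80%. At an assumed 50% vs 70% it is about 9 to 13 points, of which about 1 to 7 are due to the covariates. These figures rest on assumed covariate strengths, since the plan calls the factors only potential, and on 68 evaluable patients per arm. They concern the binary outcome with likelihood-ratio or Wald tests. The gain for the 0–4 score, and for the penalised model recommended below, was not computed.

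The documents do not support reading this as a flaw that could overturn the main result, or as a reason to adjust for all seven listed factors. Adjusting for volume or insertion time could remove part of the arm effect.

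**What to change.** In Statistical analysis, add for each arm contrast:

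- A logistic model for CMS score 1 or below with arm, sex, continuous BMI and prior abdominal or pelvic surgery. Use no P-value selection and no covariate arising after randomisation.
- Firth penalisation, with penalised-likelihood tests and intervals rather than Wald, so that an arm near 0% or 100% does not break the fit.
- The standardised risk difference with 95% CI as the reported effect.
- Fisher's exact test as the test for any contrast with an empty or near-empty cell, with the cell-count threshold written into the SAP beforehand. Otherwise keep Fisher and Kruskal-Wallis as supportive tests.
- A proportional-odds model on the same covariates for the 0–4 score, reported beside Kruskal-Wallis.

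Name sex, BMI and prior surgery in the list of recorded information. Keep the risk-factor regression, labelled exploratory.

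The cost is SAP wording and a little more SAS programming. The planned regression already needs these data. The downside is a model-based rather than exact P value.

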### **Sample size estimation**

We performed an observational study focusing on left colon mucus production using CMS scoring system by unblinded colonoscopist and compared either full strength normal saline (normal saline group), 1:1 mixed normal saline/water (50% saline group), or 1:3 mixed normal saline/water

(25% saline group) during WE insertion in patients undergoing routine colonoscopies in December 2020. We compared these findings with the reference WE water group which was video recorded during our previous randomized controlled trial comparing right colon adenoma miss rate using WE and CO2 insufflation. The results showed that fluid containing saline significantly reduced the mucus production compared to water alone (Table 1).

The sample size estimation is based on the assumption that WE 50% saline infusion will reduce left colon mucus score compared to WE water infusion. Mucus score reduction to  $\leq 1$  is considered clinically significant. According to our preliminary data, we estimate the proportion of subjects with CMS score  $\leq 1$  to be 50% in the WE water group. The sample size needed to show the proportion of subjects with CMS score  $\leq 1$  that can be increased to 80% by WE 50% saline infusion at a 5% alpha error level with 90% power will be 68 patients per group. To account for dropouts, incomplete procedures, and inadequate preparation, an additional 10% will be enrolled. Therefore, a total of 300 patients (75 patients in each group) will be enrolled.

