**Figure 1. Left Colon Mucus Scale (CMS) scores**

**Score 1**

**Score 2**

**Score 3**

**Score 4**

**Table 1. Left colon CMS score\* by unblinded endoscopists during WE colonoscopy**

Variable	WE/normal saline (n=17)	WE/50% saline (n=17)	WE/25% saline (n=17)	WE/ water (n=17)	P -value
CMS score, mean (SD)	0.35 (0.49)	0.94 (0.66)	1.06 (0.83)	1.88 (0.78)	<0.0001
Patients with CMS score $\leq 1$ , n (%)	17 (100)	14 (82)	13 (77)	4 (24)	<0.0001

\*Colon Mucus Scale (CMS) score: No mucus (score 0); Minimal amounts of clear mucus in thin streaks or strands (score 1); Mild opaque mucus in thin strands (score 2); Moderate opaque mucus in thicker clumps covering one side of the surface (score 3); More opaque mucus in thicker clumps covering more views of the lumen (score 4).

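### The overall four-group test does not hold error among the three WE fluids at 5% if the fluids are equal and CO2 alone differs by about 10 percentage points or more in CMS ≤1

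*Combined protocol and SAP*

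**What the plan says.** - **Primary questions.** Outcomes lists CO2 versus WE and, among WE patients, "the scores between groups using water versus 50% saline versus 25% saline".
- **Gate.** In Statistical analysis, overall P values for categorical and continuous parameters come from Fisher's "exact test and Kruskal-Wallis test, respectively". Then: "Pairwise comparisons among all groups were performed when the overall group effect was significant".
- **Level.** "The criterion for statistical significance will be a" P value below 0.05. No pairwise adjustment is stated, and no pairwise test is named.
- **Binary form of the outcome.** "For mucus production quantity, the 2-category scale (minimal [score 0-1] vs. moderate [score 2-4]) will be examined".
- **Size.** Sample size estimation bases the trial on 50% saline versus water (80% versus 50% with CMS ≤1), "at a 5% alpha error level with 90% power will be 68 patients per group". With 10% added, "a total of 300 patients (75 patients in each group) will be enrolled".
- **Prior data.** Table 1 was scored "by unblinded endoscopists during WE colonoscopy", so it has no CO2 arm.

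**The concern.** One overall test across four groups serves two primary questions. When all four groups are equal, the gate limits false findings to about 5%. It gives no such protection when three groups are equal and the fourth is not. If CO2 alone differs, it produces a significant overall test and the three fluid pairs are then compared with no further protection. The trial could then report a difference among fluids, including 50% versus 25% saline, that reflects only the CO2 arm opening the gate.

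**Working it through.** **1. The plan's own figure.** For 50% versus 80%, two-sided 5%, 90% power, pooled variance:

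n = [1.96·√(2·0.65·0.35) + 1.2816·√(0.5·0.5 + 0.8·0.2)]² / 0.30² = (1.322 + 0.821)² / 0.09 ≈ 51.0, so 52 per group, or 58 with continuity correction.

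The stated 68 is larger than its inputs require. Exact Fisher power at 68 is 95.0%. This is a separate matter and does not affect the point here. The inflation does follow: 68 × 1.1 = 74.8, so 75 per group and 300 in all. Both 68 (evaluable) and 75 (no dropout) are used below.

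**2. Inputs.**
- From the plan: four equal arms, P<0.05 throughout, Fisher's exact test for the overall categorical comparison, and CMS ≤1 as the binary outcome.
- Assumed: two-sided tests, Fisher for the pairs, the CO2 rate, and the three fluids equal. The base case of 50% is the plan's figure for water.

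**3. Quantity.** The chance of at least one false fluid difference is the sum, over all outcomes (x₁,…,x₄), of the product of the four binomial probabilities, counting only outcomes where (a) the exact 4×2 test has P<0.05 and (b) at least one of the three WE pairs has Fisher P<0.05. This was enumerated exactly: 69⁴ outcomes at 68 per arm and 76⁴ at 75.

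**4. Results, fluids equal at 50%.**

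| CO2 difference (points) | Gate opens, n=68 | False fluid difference, n=68 | Same, n=75 | With a second, three-WE-arm gate, n=68 |
|---|---|---|---|---|
| 0 | 4.9% | 3.4% | 3.6% | 3.0% |
| 5 | 8.1% | 4.0% | 4.4% | 3.3% |
| 10 | 19.5% | 5.4% | 6.4% | 3.9% |
| 15 | 41.3% | 6.8% | 8.5% | 4.5% |
| 20 | 68.5% | 7.7% | 9.7% | 4.8% |
| 30 | 98.1% | 8.0% | 10.2% | 4.8% |

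At 68 per arm, 5% is passed at about 9 points. As a plausibility check at 68: with the gate fully open, one null pair is rejected 3.2% of the time, so three pairs cannot exceed 3 × 3.2% = 9.6%. The pairs share arms, so the result is 8.0%.

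**5. Other fluid rates.** At 68 per arm the error reaches 8.7% with fluids at 35% or 65%. With fluids near 95% it stays below 5% (at most 3.5% at 68).

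**6. Other pairwise tests.** Chi-square pairs give 12.6% at 68 (fluids at 35% or 65%) and 13.2% at 75 (fluids at 50%) once the gate is open. For a Kruskal-Wallis gate with pairwise rank tests, simulation on assumed five-level score distributions (200,000 trials per setting) gave 7.4% to 11.7% at a 10-point CO2 difference and about 12% at large ones. There 5% is passed at roughly 3 to 6 points.

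**7. 50% saline versus water alone.** In the same equal-fluids setting, error on this pair stays at or below about 3.4% (68) or 4.1% (75) with Fisher. With chi-square it is about 5.2% (68, fluids at 35% or 65%) and 5.5% (75, fluids at 50%).

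**The case against.** - **The gate could be read per question.** Outcomes poses two questions, so the overall test for fluids might already be a three-group test, which would hold error at 4.6% to 4.8%. But the rule speaks of comparisons among all groups after the overall group effect. The four-group reading is the natural one, and no three-group test is stated.
- **The plan breaks its own 5%.** A reader might infer this. The documents do not support it: 5% is a per-test criterion and the alpha of one sample size contrast. Nothing promises 5% across the fluid pairs, so this is a standard brought to the plan and not a contradiction within it.
- **The main claim is compromised.** This too is tempting and unsupported. The contrast that sizes the trial stays near or below 5% (step 7). The excess comes from testing three pairs.
- **The scenario runs against the trial's own data.** Table 1 shows CMS ≤1 in 24% with water against 77% and 82% with the diluted salines. If one fluid differs from the other two, only one null fluid pair remains and there is no excess. That stands. However, Table 1 has 17 patients per group, scored unblinded, with water taken from an earlier trial. Equal fluids is also the null hypothesis of a primary question.
- **10.2% is a peak.** Correct. It needs no dropout and fluids near 50%. With fluids at 24% or 77% and 75 per arm, CO2 20 to 30 points away gives 7.8% to 8.1%.

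**Conclusion.** The point holds, conditionally. With the three fluids equal and CO2 about 10 points or more away in CMS ≤1, the written rule gives a chance of some false fluid difference above 5%: with Fisher pairs and fluids at 50%, 5.4% to 8.0% at 68 per arm and 6.4% to 10.2% at 75, for CO2 10 to 30 points away. This rests on an assumed CO2 rate (Background describes extra mucus with water-aided colonoscopy only as anecdotal), on two-sided tests, and on Fisher for the pairs, which the plan names only for overall P values. The excess is modest and limited to this configuration. It is worth correcting because it concerns a primary question and the remedy is short.

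**What to change.** Keep the four-group overall test and add to Statistical analysis, for example:

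> WE groups will be compared pairwise only if the same overall test across the three WE groups (Fisher's exact test for CMS ≤1; Kruskal-Wallis test for CMS scores) is also significant at P<0.05.

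Also name the pairwise test for each form of the outcome. If a pairwise adjustment is already intended, state it instead.

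**Effect.** With both gates on CMS ≤1, fluid error is 3.0% to 4.9% for CO2 0 to 45 points away (fluids at 50%). A three-group Kruskal-Wallis gate gave 4.9% to 5.0% in simulation. Error over all six pairs when nothing differs stays at 4.9% to 5.0%.

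**Cost.** No extra patients, and no outcome is demoted. Power for 50% saline versus water (80% versus 50%, with 25% saline at 76.5% and CO2 at an assumed 90%) falls from 95.0% to 93.9% at 68 per arm and from 96.5% to 95.9% at 75. The largest loss found, over 25% saline at 50% to 85% and CO2 at 2% to 98%, is 2.9 points (95.0% to 92.1%) at 68. If CO2 and 25% saline both sit near 65%, the planned gate alone already gives 89.1% at 68, and two gates give 88.7%. Holm over the three WE pairs after the planned gate would also control the error (2.6% to 3.4%), but power at 68 is 89.4%.

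**Limit.** The second gate does not protect the CO2-versus-WE pairs. If only water differs (50% against 80% in the other three groups), error over the CO2-versus-saline and saline-versus-saline pairs is 7.9% at 68 with or without it.

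### The P<0.1 univariable screen decides which mucus risk factors get an adjusted odds ratio, although the roughly 70 expected events would allow all seven to be fitted together

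*Combined protocol and SAP*

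**What the plan says.** The Statistical analysis section dichotomises the mucus score: "the 2-category scale (minimal [score 0-1] vs. moderate [score 2-4]) will be examined". It then lists candidates: "Potential risk factors for mucus production include female sex, lower body mass index, prior abdominal or pelvic surgery", poor preparation, and "water as the infused solution, larger volume of infusion, and longer insertion time". That makes seven.

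Logistic regression is meant to "assess which of the demographic and procedural data are independent predictors of moderate mucus production". The entry rule is that factors with a univariable P value below 0.1 "on univariate analysis will be further entered in the multivariate logistic regression analysis". Odds ratios with 95% confidence intervals "will be used to describe the influence of various factors on mucus production".

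The section gives no reason for the screen and no expected event count. It forces no factor into the model, and it plans no full model, shrinkage or allowance for selection. The list is introduced as examples and the aim refers to demographic and procedural data in general, so the candidate set is not firmly closed. The plan does not say whether infusate is one parameter (water or not) or two (one per saline strength against water).

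**The concern.** Whether a factor predicts mucus independently is a question about its adjusted association. The plan settles eligibility with an unadjusted P value. Three things follow.

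- A factor with a modest effect or low prevalence passes mainly in trials where chance has made its estimate large. Its adjusted OR is reported then and not otherwise, with an interval computed as if no selection had taken place.
- A factor whose crude association is hidden by a correlated factor can be removed before adjustment could reveal it.
- The randomised infusate, the factor of most interest, has no guaranteed place in the model.

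At stake are the adjusted ORs presented as those of independent predictors. The usual defence of such a screen is a shortage of events, so the first check is whether there is one.

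**Working it through.** **Events.** The plan states no event count for this model, so there is no figure of its own to reproduce. An event is a score of 2-4. Inputs:

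- WE water: the share with a score of 1 or lower is taken "to be 50% in the WE water group" (Sample size estimation), so the event rate is 1 - 0.50 = 0.50. The pilot (Table 1) had 4 of 17 at or below 1, so 13/17 = 0.765.
- WE 50% saline: the share "that can be increased to 80% by WE 50% saline infusion", so 1 - 0.80 = 0.20. Pilot: 3/17 = 0.176.
- WE 25% saline: no planning rate. Pilot: 4/17 = 0.235. Assumed range 0.20 to 0.35.
- Patients per group: 75 enrolled, 68 before the 10% addition.
- CO2 group: no rate given. An assumed 5-20% would add about 3 to 15 events if these patients enter the model.

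Results for the three WE groups:

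- Central: 75 x (0.50 + 0.20 + 0.235) = 70.1 events; 70.1/7 = 10.0 per parameter.
- Lowest: 68 x (0.50 + 0.176 + 0.20) = 59.6; 59.6/7 = 8.5.
- Pilot water rate: 75 x (0.765 + 0.20 + 0.235) = 90.0; 90.0/7 = 12.9.
- Highest: 75 x (0.765 + 0.20 + 0.35) = 98.6; 98.6/7 = 14.1.
- Central, infusate coded with two parameters: 70.1/8 = 8.8.

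**Effect of the screen.** Simulation with 225 WE patients, about 72 events and 2,000 trials. Assumptions: 50% female, 25% prior surgery, 15% poor preparation; continuous factors standardised; volume-time correlation 0.5; true OR 4 for water and 1.5 for each other factor. ORs are geometric means. The full-model column covers all trials; the screened column covers only trials in which the factor passed.

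| Factor | Dropped by screen | Full model OR | Screened OR |
|---|---|---|---|
| Sex | 67% | 1.55 | 2.10 |
| Prior surgery | 74% | 1.50 | 2.21 |
| Poor preparation | 78% | 1.50 | 2.44 |
| BMI | 24% | 1.54 | 1.62 |
| Volume | 4% | 1.54 | 1.55 |
| Insertion time | 3% | 1.53 | 1.53 |
| Water (true 4.0) | 1% | 4.28 | 4.15 |

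At least one real factor is dropped in 99% of trials. With a true OR of 2.0 for the six factors and 71 events, sex, surgery and poor preparation are dropped in 50%, 54% and 64% of trials and average 2.59, 2.78 and 3.12 when kept. BMI, volume and time stay at 2.03-2.05. At about 60 events the full model is still close to unbiased (1.50-1.54 for a true 1.5).

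**Coverage.** In a separate simulation at about 72 events with a true OR of 1.5, the 95% interval covers the truth in 92% of the trials in which sex is kept and 87% of those in which poor preparation is kept. The full model over all trials gives about 95%.

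**Masking.** In a scenario built so that factors mask each other, volume is significant in 58% of full-model trials and in 24% of screened trials.

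**The case against.** The strongest objection is that the table compares unlike sets of trials: selected trials for the screened model, all trials for the full one. In the same trials in which the factor passed, the full model gives nearly the same answer: 2.11 against 2.07 for sex and 2.56 against 2.52 for poor preparation. This stands. The distortion comes from reporting a factor only when it passes. Leaving the other factors out of the model adds almost nothing. A reader might infer that the screen inflates every surviving OR, or that a full model would shrink the survivors. Neither is supported: water, volume and time barely move.

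Second, most of the dropping reflects low power, which a full model does not cure. In a similar simulation with about 67 events and a water OR of 3.5, sex ends up significant in 21% of screened and 25% of full-model trials, and poor preparation in 13% and 15%. This also stands when no factor masks another.

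Third, the documents give no correlations among the factors, so masking is a possibility and not a demonstrated fact. Fourth, ten events per parameter assumes a closed list and a single infusate parameter, and the plan fixes neither. Sedative dose, abdominal compression and withdrawal time are also recorded and could be added. That is a reason to close the list; it does not justify a P-value screen.

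Finally, risk-factor modelling is neither a primary nor a secondary outcome under Outcomes, and the rule is at least stated in advance.

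**Conclusion.** The concern holds as a problem of selective reporting and possible masking in an ancillary analysis. On the plan's own rates the WE groups should yield about 70 events (about 60 to 99), so a shortage of events does not force the screen. For weak or uncommon factors such as sex, prior surgery and poor preparation, a true OR of 1.5 would typically be reported as about 2.1 to 2.4 when it is reported at all, with an interval that ignores the selection.

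These sizes depend on assumed prevalences, ORs and correlations. The near-immunity of volume and insertion time does too, since each was given an OR of 1.5 per standard deviation and the two were positively correlated.

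A reader might also infer that the set of predictors found is largely chance, or that the trial's main result is at risk. The first is too broad, because strong factors pass almost always unless masked. The second is wrong: the between-group comparisons use Fisher's exact and Kruskal-Wallis tests, and the sample size rests on two proportions. Severity is minor to moderate.

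**What to change.** Replace the sentence that sets the P<0.1 entry rule with:

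> The seven listed factors form the complete candidate set and will be entered together in one multivariable logistic model without univariable selection, with the infusate (coding stated in advance) always included. All adjusted ORs with 95% CIs will be reported whether or not significant; univariable ORs are descriptive only. If there are fewer than 10 events per parameter, Firth penalised estimation will be used.

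The coding choice matters for the last sentence. With two infusate parameters, the central estimate of 8.8 events per parameter would already call for the penalised fit.

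The change needs no new patients or data. The cost is slightly wider intervals for some factors. The gain is that every factor is reported, masked factors can show themselves, and the infusate stays in the model. It will not make weak factors easier to detect.
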